3.4 Dose Modifications

All toxicity grades below are described using the NCI Common Terminology Criteria for Adverse Events (CTCAE) version 4.0.

All appropriate treatment areas should have access to a copy of the CTCAE version 4.0. A copy of the CTCAE version 4.0 can be downloaded from the CTEP website (<http://ctep.cancer.gov>).

Afatinib will be administered at the recommended dose of 40 mg orally once daily starting on the first day of administration and continue until disease progression or unacceptable toxicity. We chose the 40 mg daily dose since the Css still remains adequate at this dose. With the 50 mg dose used in previous trials of afatinib in HER2+, patients showed poor tolerability data. High Rates of dose modification were seen in previous studies with 50 mg daily dosing.

Afatinib will not be held for hematologic toxicity, unless it is determined to be a drug-related grade 3 or 4 hematologic event.

Treatment may be delayed by 2 weeks due to toxicity. If treatment is delayed beyond 2 weeks the subject will come off study for unacceptable toxicity.

Discontinuation of afatinib for any reason for longer than 2 weeks will result in removal of the patient from this subprotocol.

The afatinib dose may be adjusted according to individual patient tolerance as outlined below.

Table 1. Dose Levels for Afatinib

Dose Level	Daily Dose/ Route	Dispensed As	Schedule
Starting dose level: 0	40 mg, PO	1 × 40-mg tablet	Daily during 4-week cycle
-1	30 mg, PO	1 × 30 mg tablet	Daily during 4-week cycle
-2	20 mg, PO	1 × 20-mg tablet	Daily during 4-week cycle

3.4.1 Treatment compliance

Records of study medication usage and doses administered will be kept during the accountability will be noted. Patients will be asked to return all unused medication.

3.4.2 Toxicity monitoring & dose modification

Patients will have clinical and laboratory assessment while on study as per the Study Calendar. No dose escalations of afatinib will be permitted.

In the event of any CTC, version 4.0 drug-related grade 3 or 4 non-hematologic adverse event(s), drug should be held until the toxicity resolves to ≤ grade 1 and then the drug should be restarted at a one dose-level reduction with the exception noted in table 2. In addition, no dose modifications will be needed for low electrolytes (Na, K, Phos, Mg) unless the grade 3 or 4 adverse event were to last >48

hours despite optimal electrolyte repletion. Please see supportive care guidelines for nausea, vomiting, diarrhea, fatigue, and rash.

Patients should be carefully monitored for clinical signs and symptoms of CHF while receiving afatinib. In the presence of clinical manifestations of CHF, discontinuation of afatinib and assessment of LVEF is recommended.

In the event of any CTC, version 4.0 drug-related grade 3 or 4 hematologic adverse event(s), the drug should be held until the toxicity resolves to \leq grade 1 and then the drug should be restarted at a one dose-level reduction.

3.4.3 Dose reduction for afatinib

Intra-patient dose reduction by 1, and if needed 2, dose-levels will be allowed depending on the type and severity of toxicity encountered provided that criteria for patient withdrawal from study treatment have not been met. Intrapatient dose re-escalation is not allowed.

All intra-patient dose reductions are relative to the lowest dose level of the current cycle.

Recovery to acceptable levels of toxicity must occur within 2 weeks to allow continuation in the study.

No more than 2 dose reductions are permitted for any patient. If further dose reduction is required, the patient must be removed from the study.

The following table describes the recommended dose modifications for study treatment associated toxicity:

Table 2. Dose Modification for Afatinib

Toxicity	Grade 1	Grade 2	Grade 3	Grade 4
Non-hematologic Toxicity (except specific toxicities mentioned below) ^{a,b,c}	Continue at the same dose level.	Continue at the same dose level.	Withhold dose until toxicity is grade ≤ 1 or has returned to baseline. Then reduce the dose by 1 level and resume treatment.	Withhold dose until toxicity is grade ≤ 1 or has returned to baseline. Then reduce the dose by 1 level or discontinue treatment (discretion of the investigator).
Cardiac Toxicity	Continue at the same dose level.	Continue at the same dose level except for asymptomatic decrease of LVEF by an absolute value of 20% (or more) and to $<$ institutional LLN. Withhold dose until toxicity is grade ≤ 1 . Then reduce dose by 1 level and resume treatment.	Discontinue study treatment.	Discontinue study treatment.
Renal Toxicity	Continue at the same dose level.	Withhold dose until toxicity is grade ≤ 1 . Then reduce dose by 1 level and resume treatment.	Withhold dose until toxicity is grade ≤ 1 . Then reduce dose by 1 level and resume treatment.	Withhold dose until toxicity is grade ≤ 1 . Then reduce dose by 1 level and resume treatment or discontinue treatment (discretion of the investigator).
Diarrhea	Continue at the same dose level. ^b	Continue at the same dose level unless diarrhea persists for 2 or more days despite adequate anti-diarrheal medication or hydration. Withhold dose until toxicity is grade ≤ 1 . Then reduce dose by 1 level and resume treatment.	Withhold dose until toxicity is grade ≤ 1 . Then reduce dose by 1 level and resume treatment.	Withhold dose until toxicity is grade ≤ 1 . Then reduce dose by 1 level and resume treatment.
Rash (Papulopustular, pustular, acneiform, maculo-papular) ^d	Continue at the same dose level.	Continue at the same dose level unless rash persists and is intolerable or worsens over > 7 days. If this occurs: Withhold dose until toxicity is grade ≤ 1 . Then reduce dose by 1 level and resume treatment.	Withhold dose until toxicity is grade ≤ 1 . Then reduce dose by 1 level and resume treatment.	Discontinue study treatment
Drug-induced hepatic impairment	Continue at the same dose level.	Continue at the same dose level.	Withhold dose until toxicity is grade ≤ 1 or has returned to baseline. Then reduce the dose by 1 level and resume treatment.	Discontinue study treatment

Ulcerative keratitis	Continue at the same dose level.	Continue at the same dose level.	Withhold dose until toxicity is grade ≤ 1 or has returned to baseline. Then reduce the dose by 1 level and resume treatment.	Discontinue study treatment
Interstitial Lung Disease	If a patient develops respiratory problems consistent with possible interstitial lung disease (ILD), afatinib is to be withheld pending a diagnostic evaluation. Afatinib will be discontinued if a diagnosis of ILD is confirmed.			

- a. *No dose modifications will be needed for low electrolytes (Na, K, Phos, Mg) unless the grade 3 or 4 adverse event were to last >48 hours despite optimal electrolyte repletion*
- b. *See supportive care for diarrhea in Section [3.5.1](#)*
- c. *Nausea and vomiting should be graded after maximal medical management*
- d. *See supportive care for rash in Section [3.5.1](#)*

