Keratitis and ulcerative keratitis have been reported with the EGFR inhibitors. In 6,002 afatinib treated patients, 39 (0.6%) cases were identified.

Effect on QTc

A phase II study in patients with advanced solid tumors investigated the effect of afatinib on the QTc interval. Afatinib at doses of 50mg daily did not prolong the QT interval or the heart rate corrected QT interval (QTcF). It did not affect heart rate. No other clinically meaningful changes in QTcF or ECG endpoints were observed.

Events of cardiac dysfunction/LVEF decrease

Left ventricular ejection fraction (LVEF) decrease has been reported with agents targeting HER2, in particular with the monoclonal antibody, trastuzumab. In the phase IIb/III trial in advanced NSCLC using afatinib 50mg, 4 (1.0%) afatinib treated patients vs 1 (0.5%) placebo patients experienced an AE of cardiac failure, cardiopulmonary failure, hepatic congestion or left heart failure. This was a non-significant difference (HR 1.32, 0.14-12.50).³⁷ In study 1200.32, with 40mg of afatinib, the frequency of these AEs was 2.6% in the afatinib arm vs 0.9% in the chemotherapy arm. This was not significantly increased when corrected for time at risk (HR 1.18, 0.12-11.39). Furthermore, the heart failure or LVEF decrease events were all grade 2 or lower.³⁵

2. Selection of Patients

Each of the criteria in the checklist that follows must be met, along with the eligibility in the MATCH Master Protocol, in order for a patient to be considered eligible for this study. Use the checklist to confirm a patient's eligibility. For each patient, this checklist must be photocopied, completed and maintained in the patient's chart.

In calculating days of tests and measurements, the day a test or measurement is done is considered Day 0. Therefore, if a test is done on a Monday, the Monday four weeks later would be considered Day 28.

ECOG-ACRIN Patient No. _____

Patient's Initials (L, F, M) _____

Physician Signature and Date _____

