3.6 Duration of Agent-specific treatment

In the absence of treatment delays due to adverse event(s), treatment may continue until one of the following criteria applies:

- Extraordinary Medical Circumstances: If at any time the constraints of this protocol are detrimental to the patient's health, protocol treatment should be discontinued. In this event submit forms according to the instructions in the MATCH Forms Packet.
- Patient withdraws consent.
- Patient experiences unacceptable toxicity.
- Non-protocol therapies are administered.
- Disease progression

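### The grade 2 cardiac cell of Table 2 keeps afatinib at full dose for symptomatic heart failure, while Section 3.4.2 recommends stopping; the subprotocol does not say which governs

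*Protocol*

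**What the plan says.** Two parts of Section 3.4 of the Protocol deal with cardiac events on treatment.

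- **Section 3.4.2** asks sites to watch for signs and symptoms of CHF and then states: "In the presence of clinical manifestations of CHF, discontinuation of afatinib and assessment of LVEF is recommended". No toxicity grade is attached.
- **Section 3.4.3, Table 2, cardiac row** works by grade. Grade 1 continues at the same dose. Grade 2 reads "Continue at the same dose level except for asymptomatic decrease of LVEF by an absolute value of 20% (or more", and the fall must also reach below the institutional lower limit of normal. When both conditions are met, the drug is held until grade 1 or better and resumed one level lower. Grades 3 and 4 stop treatment.

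Table 2 is introduced with "The following table describes the recommended dose modifications for study treatment associated toxicity", so both instructions are worded as recommendations.

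**The concern.** The grade 2 exception is limited to asymptomatic falls in LVEF, so a symptomatic grade 2 event stays under the continue instruction. That reverses the expected order: a silent LVEF fall of sufficient size leads to a hold and a reduction, while heart failure with symptoms carries on at full dose. For that same event Section 3.4.2 recommends stopping and measuring LVEF. A site that works from the table, as sites often do for dose decisions, would take the opposite action to the one recommended in the preceding text.

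The symptom rule also carries much of the cardiac protection here. Section 2.1.4 requires no LVEF before treatment unless left ventricular dysfunction is already known, and the study calendar in Section 4.1 asks for on-treatment echocardiography or nuclear study only when clinically indicated. A patient without a baseline value has no reference against which to measure a 20% absolute fall, so the table's one grade 2 exception may not be assessable for that patient.

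**Working it through.** No figure in the plan is at issue. The check sets the two instructions side by side and then looks for anything that reconciles them.

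**1. Actions for clinical CHF, by grade**

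| Grade assigned | Table 2 cardiac row | Section 3.4.2 | Result |
|---|---|---|---|
| 1 | Continue | Stop, assess LVEF | Not established: the documents do not show that clinical CHF can be graded 1 |
| 2 | Continue (the only exception is asymptomatic) | Stop, assess LVEF | Conflict |
| 3 | Discontinue | Stop, assess LVEF | Agree |
| 4 | Discontinue | Stop, assess LVEF | Agree |

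One cell of four is shown to conflict.

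**2. Can symptomatic cardiac events fall at grade 2?** The grading definitions (CTCAE version 4.0) are not reproduced in the Protocol. Two things in the text point to yes. First, the word asymptomatic in the grade 2 cell would be unnecessary if grade 2 covered only silent events. Second, Section 1.1.3 reports that in the 40 mg lung cancer trial "the heart failure or LVEF decrease events were all grade 2 or lower". This second point is weak evidence. It pools heart failure with LVEF decrease, does not say how many events were symptomatic, and comes from non-small cell lung cancer, which Section 2.1.10 excludes. It shows only that the reported events lay below the grades at which the two texts agree.

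**3. Does anything reconcile the two texts?**

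- The one pointer from Section 3.4.2 to the table, "with the exception noted in table 2", belongs to the rule for grade 3 or 4 non-hematologic events, not to the CHF sentence.
- The four footnotes to Table 2 cover electrolytes, diarrhea, nausea and vomiting, and rash.
- The proviso in Section 3.4.3 about withdrawal criteria limits when a dose may be reduced. It does not address the continue instruction.
- Section 3.6 lists unacceptable toxicity in general and does not name CHF.
- The interstitial lung disease row shows that the table can carry a rule that ignores grade: "Afatinib will be discontinued if a diagnosis of ILD is confirmed". The cardiac row has no such line.

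**4. Scale.** The Protocol gives no rate for symptomatic grade 2 CHF. For a wider group of cardiac failure terms, Section 1.1.3 gives 2.6% in the 40 mg arm. Assuming that this lung cancer rate carries over, and taking the accrual goal of 70 from the Schema, 70 × 0.026 = 1.82, or about two patients with any event of that group. Symptomatic grade 2 CHF would be a subset of these. The figure is an order of magnitude only.

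**The case against.** The strongest defence is that the texts work in sequence. Section 3.4.2 responds to a presentation: stop and measure LVEF. Table 2 then disposes of the event once it has been graded and attributed to study treatment. Section 3.4 allows for short stops, since "Discontinuation of afatinib for any reason for longer than 2 weeks will result in removal of the patient from this subprotocol", so a discontinuation need not be permanent. A second defence is that a rule for one named syndrome outranks a rule for a whole toxicity category, and that the table's exception is confined to asymptomatic falls because symptomatic failure had just been dealt with.

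Both readings are plausible, and a careful clinician would probably adopt one of them. Neither is stated. On the sequential reading the grade 2 cell still returns a patient with symptomatic CHF to the same dose, while the silent LVEF fall is reduced. The general sentence in Section 3.5.1 about reducing the dose after a pause might lower the restart dose, but the cardiac cell neither says so nor refers to it.

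Four stronger inferences are tempting and are not supported:

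- *The grade 1 cell conflicts as well.* This needs clinically manifest CHF to be gradable as 1, which the documents do not show.
- *The protocol compels continued dosing.* It does not. Both texts are recommendations, and Section 3.6 says "If at any time the constraints of this protocol are detrimental to the patient's health, protocol treatment should be discontinued".
- *Nothing in the trial settles precedence.* The subprotocol is to be used with the MATCH Master Protocol, which was not available here. The absence can be stated only for this subprotocol.
- *Efficacy conclusions are affected.* Nothing in the documents supports that.

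**Conclusion.** The point holds as an internal inconsistency in a safety rule, wrong as written and of minor severity. For symptomatic CHF graded 2, the cardiac row says to continue at the same dose, Section 3.4.2 recommends stopping and assessing LVEF, and this subprotocol does not rank them.

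The conclusion rests on a literal reading of the grade 2 cell and on symptomatic CHF being gradable as 2, which the cell's own wording suggests but the documents do not define. The number of patients would be small. The specific-over-general reading and Section 3.6 lower the practical risk but do not tell a site which instruction to follow.

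**What to change.** Add one line to the cardiac row of Table 2, in the grade-independent form already used for interstitial lung disease, to this effect: *Clinical manifestations of CHF, regardless of grade: stop afatinib and assess LVEF, as recommended in Section 3.4.2; this takes precedence over the grade-based continue instruction.*

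This keeps the strength of Section 3.4.2 as a recommendation and creates no new mandatory stop. The two-week limit in Section 3.4 still decides when a patient leaves the subprotocol. The cost is a one-line addendum with no added patients or procedures. The downside is that a few patients may stop earlier than under the present table.

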3.5 Supportive Care

3.5.1 All supportive measures consistent with optimal patient care will be given throughout the study.

After a treatment pause the dose of afatinib should be reduced according to the dose reduction scheme in Table 1. The occurrence of nausea and/or vomiting will be recorded in the AE section of the eCRF.

Management of Diarrhea

Close monitoring and proactive management of diarrhea is essential for successful treatment of patients with afatinib. Early and appropriate intervention can prevent the development of more severe diarrhea. In most cases, loperamide (Imodium) controls diarrhea caused by afatinib.

The recommendations for management are as follows:

If any diarrhea is experienced (CTCAE Grade 1), two 2 mg loperamide tablets (total dose 4 mg) should be taken immediately, followed by one 2 mg tablet with every loose bowel movement, up to a maximum daily dose of 8 tablets (16 mg). Other anti-diarrheal medications that could be used include: Lomotil (5 mg, four times a day), or tincture of opium (15-20 drops orally every 4 hours) or octreotide (150 to 300 micrograms SQ twice a day).

Oral hydration is important regardless of severity of diarrhea; appropriate rehydration (1.5L/m²/day plus equivalent of actual fluid loss) and electrolyte replacement should be recommended in the event of CTCAE Grade 2 and Grade 3 diarrhea.

Management of Rash

A proactive and early approach to management of rash is crucial. Rash can be managed by a variety of treatment options to relieve symptoms and reduce the rash. The recommendations for management are as follows:

General/Prevention: strict sun protection; use of a sunscreen of Sun Protection Factor 15 (SPF 15) or higher, preferably containing zinc oxide; use of a thick, alcohol-free emollient cream.

CTCAE Grade 1 rash: mild rash may not need treatment. However, if treatment is considered necessary, topical hydrocortisone (1% or 2.5%) cream and/or clindamycin 1% gel/lotion can be used.

CTCAE Grade 2 rash: relief from major symptoms caused by CTCAE Grade 2 skin related adverse events should be achieved by a combination of local and systemic therapies including:

- 1) Systemic antibiotics (e.g. doxycycline or minocycline etc.).
- 2) Topical treatment (e.g. hydrocortisone 2.5% cream, clindamycin 1% gel/lotion, pimecrolimus 1% cream). And / or 1) Antihistamines (e.g. diphenhydramine, etc.)
- 3) Oral corticosteroid (low dose and short term i.e., < 10 days)

treatment) may be added at investigator's discretion.

Systemic and topical treatment should be initiated at the start of CTCAE Grade 2 rash and continued until improvement or resolution to CTCAE Grade ≤ 1 . If grade 2 rash persists for ≥ 7 days despite treatment and is poorly tolerated by the patient, the investigator may choose to pause treatment for up to 14 days followed by a reduction in the dose of afatinib according to the dose reduction scheme in Table 2.

Management of Fatigue

For intolerable fatigue (grade ≥ 3), the next cycle of treatment may be delayed by up to two weeks.

Management of Interstitial Lung Disease

Although quite rare, interstitial lung disease (ILD) is a class effect of EGFR TKIs and can be life threatening. Therefore, patients should be monitored closely for symptoms consistent with ILD, such as new onset dyspnea without an obvious cause. Chest CT should be obtained to look for interstitial fibrotic changes if ILD is suspected. In the event that ILD is suspected, drug treatment should be discontinued and the patient should receive appropriate medical management and supportive care. Although there is no established treatment, systemic corticosteroids are often administered. Afatinib should not be restarted in those patients suspected of having drug-related ILD and the subject should be removed from the study.

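### The Section 3.5.1 fatigue sentence is later and weaker than the hold-and-reduce rule that governs drug-related grade 3 or 4 fatigue, and Section 3.4.2 points sites to it

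*Protocol*

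**What the plan says.** **The general rule.** Protocol Section 3.4.2 says of any "drug-related grade 3 or 4 non-hematologic adverse event(s), drug should be held until the toxicity resolves to" grade 1 or lower; the drug is then restarted one level down, apart from the exceptions in Table 2. The section adds a carve-out for low electrolytes.

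**Table 2.** Section 3.4.3 introduces it this way: "The following table describes the recommended dose modifications for study treatment"-associated toxicity. Its general row is labelled "Non-hematologic Toxicity (except specific toxicities mentioned below". At grade 3 the dose is withheld until grade 1 or lower, or baseline, and then lowered one level. At grade 4, after withholding: "Then reduce the dose by 1 level or discontinue treatment (discretion of the investigator". Separate rows cover cardiac, renal and hepatic toxicity, diarrhea, rash, ulcerative keratitis and interstitial lung disease. Fatigue has none.

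**The pointer.** Later in the same paragraph as its hold rule, Section 3.4.2 says: "Please see supportive care guidelines for nausea, vomiting, diarrhea, fatigue, and rash".

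**The fatigue text.** The whole of Management of Fatigue in Section 3.5.1 is one sentence: for intolerable fatigue, defined as grade 3 or higher, "the next cycle of treatment may be delayed by up to two weeks".

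**Surrounding rules.** Section 3.1 has afatinib taken every day without a break through each 28-day cycle. Section 3.4 caps any treatment delay at two weeks. Section 3.5.1 opens by requiring a dose reduction after any pause.

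**The concern.** Afatinib is a continuous daily drug, so delaying the next cycle is not the same as stopping the drug when the event occurs. Read literally, the fatigue sentence does not ask a site to stop dosing in the current cycle, and it makes even the later delay optional. Its only content is a dosing instruction. The diarrhea and rash text in Section 3.5.1, by contrast, is mainly treatment advice.

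A site that follows the Section 3.4.2 pointer therefore arrives at something that looks like a fatigue-specific dose rule. Two sites could handle the same event differently, one holding and reducing and the other continuing at full dose, and each could cite protocol text. What is at stake is patient safety and consistent exposure across sites. No endpoint, analysis or sample size figure is touched.

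**Working it through.** The protocol states no figure on this point to reproduce. The check is a side-by-side reading, followed by simple dose arithmetic.

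**1. Which rule covers fatigue?** Section 3.4.2 covers any drug-related grade 3 or 4 non-hematologic event and names two sources of exception: Table 2 and low electrolytes. Fatigue is in neither. Table 2's general row takes everything without a row of its own, so fatigue falls there.

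**2. How does the protocol link the five toxicities in the pointer?** Four appear in Table 2 or its footnotes. Diarrhea and rash have rows, with footnotes back to Section 3.5.1 (for example "See supportive care for diarrhea in Section" 3.5.1). Nausea and vomiting are in a footnote: "Nausea and vomiting should be graded after maximal medical management". Fatigue is the only one with neither a row nor a footnote, and the fatigue paragraph does not refer back to Table 2.

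**3. Element by element, for drug-related fatigue of grade 3 or higher:**

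| Element | Section 3.4.2 and Table 2 | Section 3.5.1 | Conflict? |
|---|---|---|---|
| When to act | At the event | Next cycle | Yes |
| Force | Should hold (3.4.2); withhold (Table 2) | May delay | Yes |
| Dose after a pause | One level lower (grade 4: or discontinue) | Reduced, by the section's opening rule | No conflict on the reduction |
| Dose if no pause is taken | Does not arise, since the drug is held | No reduction triggered | Follows from the first two rows |
| Maximum delay | Two weeks (Section 3.4) | Two weeks | No |

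**4. Extra doses if a site acts on Section 3.5.1 alone.** Inputs: a 28-day cycle (Section 3.1) and Cycle 1 toxicity checks on Days 8 and 15 (Section 4.1). If grade 3 fatigue is found on Day d and that day's dose has been taken, the doses left in the cycle are 28 − d.

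- Day 8: 28 − 8 = 20
- Day 15: 28 − 15 = 13

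Under Section 3.4.2 and Table 2 the number is 0 until recovery. These are upper bounds for findings at those two visits. For fatigue found at the check just before a new cycle, the next cycle is the one about to start. The timing gap then closes and only the optional wording remains.

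**5. Dose if no pause is taken.** Starting dose 40 mg, level −1 is 30 mg (Section 3.4, dose-level table): (40 − 30)/40 = 25% lower under Table 2.

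**6. How common is fatigue?** The adverse event list in Section 3.3 puts it in the column for events seen in more than 20% of patients. If that frequency carries over to the accrual goal of 70, then 0.20 × 70 = 14, so more than 14 patients would be expected to have fatigue of any grade. The protocol gives no grade 3 rate, so the number who would meet the ambiguity is left unestimated.

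**The case against.** The strongest reply is that the protocol already shows which rule governs. The absence of a fatigue row means no exception was made, so the general row applies unchanged. The fatigue sentence sits under supportive care, is permissive, does not tell anyone to keep dosing, and resembles the general permission in Section 3.4 to delay for toxicity, which nobody reads as undoing the hold rule. It is also not limited to drug-related fatigue, so it has a use where Section 3.4.2 does not reach. And a site that follows the pointer has just read, in the same paragraph, that the drug should be held.

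Most of this stands. A reader might infer that Section 3.5.1 overrides Section 3.4.2, or that nothing in the protocol indicates which rule controls. The text supports neither inference: the pointer does not say that the supportive care text replaces the hold rule, and the scope of Section 3.4.2 and the general row favors the hold rule. A reader might also infer that the two texts conflict on the restart dose or on the length of delay. They do not once a pause is taken.

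What the reply does not remove is the fatigue sentence itself. It expressly covers the same grades, does not set drug-related fatigue apart, and gives a later and weaker instruction at the place to which sites are sent. The opening rule of Section 3.5.1 on reducing after a pause does not help where the optional pause is not taken.

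**Conclusion.** The inconsistency is real but narrow. For drug-related fatigue of grade 3 or higher, Section 3.5.1 departs from Section 3.4.2 and Table 2 in timing and in force. Section 3.4.2 with Table 2's general row is the better reading. The defect is that its own pointer leads to wording which, followed as written, would allow dosing to continue to the end of the cycle with no reduction.

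The size is at most 20 extra doses after a Cycle 1 Day 8 finding or 13 after Day 15, and a dose of 40 mg rather than 30 mg if no pause follows. Both figures assume a site that acts on the fatigue sentence alone, so they describe a worst case and not expected practice. A reader might want a count of misdosed patients; the documents support none, since neither the grade 3 rate nor the share of sites that would misread the text is given. This is a safety instruction worth correcting. It is not a flaw in the design or the analysis.

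**What to change.** Replace the fatigue sentence in Section 3.5.1 with:

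> For drug-related grade 3 or higher fatigue, withhold afatinib at onset and modify the dose per Section 3.4.2 and Table 2, subject to the 2-week limit in Section 3.4. For grade 3 or higher fatigue not attributed to afatinib, a delay of no more than two weeks is allowed.

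This keeps the permissive delay for the cases that Section 3.4.2 does not cover.

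Optionally, align the grade 2 rash text in Section 3.5.1 with Table 2 in the same addendum. Section 3.5.1 leaves the pause to the investigator's choice and omits worsening as a trigger, whereas Table 2 says to withhold and includes it. The reduction step already agrees.

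The cost is one sentence of addendum wording, or two with the rash edit. Visits, data collection and sample size do not change.
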